Cover page with official title: Gut Microbiome and Blood Markers After Habitual Herbal Tea Consumption (SRTT) (ID, INSERT)

NCT number:

Document date: 12 May 2023

Well-being and health Assessment Research Unit (WARU),
[name],
Aberystwyth University,
[name],
Aberystwyth,
Ceredigion.
[name]

Table of Contents

- 1) Introduction**
- 2) Statement of Purpose**
- 3) Investigational Product**
- 4) Investigational Product Safety**
- 5) Study Design**
- 6) Patient Risks**
- 7) Benefit To Subjects**
- 8) Privacy Confidentiality**
- 9) Safety Monitoring**
- 10) Data Analysis and Statistics**
- 11) References**

1) Introduction

TeTrimTeas intends is to establish a long-term cooperative with local growers and producers who will become partners in the business, with profit share to local growers and producers. The overall aim of the company is to produce quality, science-based botanical/herbal teas to improve health and wellbeing, growing as many of the ingredients locally and organically, to reduce food-to-fork miles within the decarbonisation and sustainability agendas in Wales.

TeTrimTeas have created herbal green tea blends, improving on existing Chinese formulation, and would like to test it as 'health tea'. The recruited cohort will be randomised into one of three intervention teas (green tea control, senna herbal mix and rhubarb root herbal mix). They would like to explore if consumption of the teas for 21 days has an impact on digestion and potentially help control weight gain.

Aberystwyth University will use high resolution metabolomics to investigate the chemical composition of capillary blood samples, in particular the short chain fatty acids. They will also assess lipid composition in capillary bloods and the microbiome of stools. Diet data, stool consistency and anthropometric measurements will be collected pre and post intervention. Results will advance product development and data would be used in grant applications into the health benefits of the herbal teas.

2) Statement of Purpose

The teas contain green tea, which contain low amount of caffeine. In addition, the intervention teas contain honeysuckle flower, Cassia seed, lotus leaf, five-leaf ginseng and hawthorn fruit, and senna leaf or rhubarb root. If large quantities of the herbal teas are consumed in one go, a laxative effect may occur. This product is not hazardous. This product is free of the following components and their products thereof: cereals containing gluten, crustaceans, eggs, fish, peanuts, soybeans, milk (including lactose), nuts, celery, mustard, sesame seeds, sulphur dioxide and sulphite, lupin and molluscs, in compliance with Regulation (EC) No. 1169/2011. This product does not contain added colorants. The teas are vegan, and they are produced and stored in a food grade facility.

5) Study Design

5.1) Objectives of the Study

The **primary objective** of this proposal is to test our hypothesis that rhubarb root tea consumption over 21 days in a healthy human cohort will decrease total Cholesterol, Low-Density Lipoprotein (LDL) cholesterol, Triglycerides (Trig) and non-HDL in capillary bloods (plasma) when compared with baseline, and when compared with the senna and green tea arms after 21 days.

A **secondary objective** of this proposal is to test our hypothesis that rhubarb root tea consumption over 21 days will improve or maintain High-Density Lipoprotein (HDL) cholesterol in capillary bloods (plasma) when compared with baseline, and when compared with the senna and green tea arms after 21 days.

Researchers will measure diet quality using the Prime Diet Quality Score (PDQS), a food-based diet quality index (Gicevic, Mou, Bromage, Fung, & Willett, 2021). It is hypothesized that the score will increase from baseline, indicating an improved diet after consumption of the intervention teas, particularly the Rhubarb root tea when compared with the senna and green tea.

Researchers will explore changes in short chain fatty acids concentrations in plasma measured using Gas Chromatography-Flame Ionization Detection

Researchers will measure stool consistency using the Bristol Stool Form Scale, to monitor laxative effects.

Researchers will employ 16S rRNA gene amplicon sequencing (via Illumina) to characterise the bacterial composition of the faecal samples. From this, alpha and beta indices representing community structure will be compared between the pre and post intervention samples (and between treatments) using classical statistical approaches such as permutational multivariate analysis of variance and linear regression analysis. Researchers will monitor the microbiota to define if there are any key responding microbes that correlate with health measurements (weight, BMI other biomed measurements etc) that are boosted or depleted in response to the tea.

5.2) Subject Selection

55 participants, over 18 years, mixed gender, mixed ethnicity.

5.3) Inclusion Criteria:

- Consenting adults >18 y Age
- Commit to fasting capillary blood collection.
- Commit to stool sampling collection.
- Able to refrain from taking any over-the-counter medication or herbal supplements during the diet monitoring and experimental periods.
- Able to prepare and consume the tea during the experimental days, after the last meal/snack of the day and not to consume anything afterwards.
- Fill in diet questionnaires and stool ranking.
- Able to inform the researcher if any antibiotics or heavy alcohol is consumed over the intervention period.

5.4) Exclusion Criteria

- Serious health conditions that require daily long-term medications (including immunosuppressants)
- A history or current diabetes, lung issues, gut inflammation (Crohn's, IBD), digestive disorders
- Diagnosed with a serious health condition within the last 12 months.
- Pregnant
- Play sports at a high level (more than 7h/week or 1h/day)
- Smoking
- consume high dose of alcohol > 21 unit per week for men and > 14 units per week for women.
- Food allergy /food intolerance/ eating disorder or are on a specially prescribed diet.

5.5) Covid Exclusion criteria

- Showing (or anyone within the household) any COVID-19 symptoms (see COVID-19 basic health screen) *
- Higher risk or vulnerable from coronavirus or live with someone at a higher risk of a severe illness from COVID-19 (over 70, undergoing cancer treatment, high risk of getting infections).
- Had a letter from the NHS advising you to shield (isolate).
- Had been at risk of exposure to COVID-19 such as travel, contact with someone with COVID-19, been exposed to the virus, or has been asked to self-isolate by the track and trace system.
- Serious health conditions that require daily long-term medication.

*If the potential participant has had COVID-19 previously (and are fully recovered and not within isolation) then they are eligible to join the study.

5.6) Study Design

After pre-induction over the phone, if the participant is eligible and still interested, the researcher will firstly run through an induction session. This can be done by phone or Teams (whatever suits the

GDPR: For the data the Welsh Government requires, Welsh Government is the data controller and Aberystwyth University (WARU) is the data processor. For any other data, including sensitive personal data, the data controller and the data processor is Aberystwyth University (WARU).

participant best). The study is randomised so the participant will be allocated into one of three groups. This will be double blinded so neither the participant nor the researcher will know what group the participant have been allocated into. Information can be disclosed at the end of the study if the participant desires. The participant will need to come to WARU or Trimsaran Community Health Centre for a capillary blood sample collected from the finger using a lancet. The participant will need to collect a stool sample using kits and toilet facilities provided.

Induction

The researcher will firstly run through how the researcher are working safely during coronavirus (COVID-19). Then the researcher will introduce the participant to all the study materials the participant will experience during the experimental session.

Materials will include:

- Tea bags for the 21 days
- Stool collection kit and Bristol stool scale
- Blood collection kit
- Prime Diet Quality Score (PDQS) questionnaire

The researcher will run through the logistics of WARU or Trimsaran Community Health Centre visits and organise dates.

The experimental sequence:

‘Monitoring’ period (two days before the study)

The researcher would ask the participant to refrain from taking any over-the-counter medication (such as ibuprofen, paracetamol, aspirin, cough/ cold remedies) or herbal supplements, and to let the researchers know if the participant find that it is necessary to take any such medication during the trial.

Experimental session- 21 days

Morning: The participant will come to WARU or Trimsaran Community Health Centre at the pre-organised timeslot to allow the researchers to collect a fasted capillary (fingerpick) blood samples and stool sample (which may be brought in with the participant). The participant may consume their breakfast after the visit. The participant will also collect the allocated tea bags. The researcher will also take the participants the weight and height. The researcher will ask the participant to record their stool consistency using the Bristol stool scale and record their diet using the PDQS questionnaire.

Over 21 days: the researchers would like the participant to consume a cup of hot-infused tea after their last meal/snack of the day (post 6pm) daily, for 21 days. The researcher would ask the participant not to consume anything after the tea. In a cup/mug the researcher would ask the participant to place a 2.5g tea bag and add 190ml of hot water (80-100°C) and stir clockwise 10 consecutive times to allow for optimal infusion and then allow to brew for 5 minutes, before removal.

Whilst undergoing the experimental sessions, if necessary, the researcher will be easily contacted by email, Teams or phone.

GDPR: For the data the Welsh Government requires, Welsh Government is the data controller and Aberystwyth University (WARU) is the data processor. For any other data, including sensitive personal data, the data controller and the data processor is Aberystwyth University (WARU).

After the experimental period:

Morning of the final visit. Please come to WARU or Trimsaran Community Health Centre at the pre-organised timeslot to allow the researchers to collect a fasted capillary (fingerpick) blood samples and stool sample (this may be brought in with the participant). The researcher will also take the participants the weight and height. The researcher will ask the participant to record their stool consistency using the Bristol stool scale and record their diet using the PDQS questionnaire. The participant may consume their breakfast after their visit. Afterwards, the participant can go back to their 'normal' eating pattern.

Post study

The researcher would like the participant to fill in an additional PDQS questionnaire at least 21 days after the experimental period and provide their weight.

6) Participant Risks

For the capillary blood samples, some people may feel nervous and on rare occasions dizziness may occur. Alongside green tea, the intervention teas may contain honeysuckle flower, Cassia seed, lotus leaf, five-leaf ginseng, hawthorn fruit, senna leaf and rhubarb root. The herbal teas contain low amount of caffeine and, if large quantities of the herbal teas are consumed in one go, a laxative effect may occur. The tea ingredients have already been tested for any adverse effects in a human cohort, however if any negative effects occur, participants are asked to refrain from continuing in the study.

7) Benefits to participant

There is no financial gain for participants if they decide to join this study. They will allow the researchers to gain important insight into the action of health teas using a combination of techniques including metabolomics, gut microbiome analysis and lipid analysis. This will be the first time this type of research will have been conducted and will be a valuable pilot study before they can investigate any human health benefits in the future. Researchers will provide participants with tea for the experimental days.

8) Privacy/confidentiality

Participants are informed that only the researchers involved with the study will be able to look at the information they provide. Specific details and personal identifiers will only be available to the researchers. At the end of the study, any information relating to participants will be made pseudonymous (coded without their name associated). Participants will not be identifiable in any publication that may arise from this research. Electronic files will be kept in a logical manner and will always be kept grouped within specific folders and password protected. All data storage is using the AU network and backed up. Once the raw data has been extracted from a paper version onto a computer, the paper will be destroyed via a paper shredder or in confidential waste bags to ensure the participant's confidentiality. There may be times when keeping paper forms are necessary (consent forms), but in this case the paper versions will be kept in a locked filing cabinet. All files that are stored on the WARU share drive will always be protected with a secure password. Setting passwords will automatically encrypt the document and will not allow any unauthorised access to the data. The Gatekeeper of the passwords delivers the passwords by encrypted emails. When sharing

GDPR: For the data the Welsh Government requires, Welsh Government is the data controller and Aberystwyth University (WARU) is the data processor. For any other data, including sensitive personal data, the data controller and the data processor is Aberystwyth University (WARU).

data, the researchers will be using the WARU shared drive, which will be kept organised, and all documents will be in relevant folders and password protected if containing confidential information. The only people that will have access to the share drive are WARU staff, directly involved with the project. When sharing data between researchers, this will be done by uploading the document to the WARU share drive. Documents will not be sent directly via email. All biofluids are stored in a locked freezer. Key is kept by the gatekeeper.

9) Safety Monitoring

9.1) Participant:

If a participant, or a member of their family/household become unwell during the study, then they are pre-warned to alert a member of the research team immediately using the contact information they have been provided. Participation in the study will be suspended immediately until further discussion with the research team has taken place. If they become unwell at any point and need medical assistance, they are advised to contact 111 and seek advice from the NHS health sector or their doctor's surgery. The researchers have a duty of care towards them and can help monitor their health remotely over 14 days and will help in any way they can.

9.2) Data:

Each computer that belongs to the WARU team is programmed with the university network. Therefore, to gain access to the computer each member of staff will have a unique password to gain access to their own desktop account. Staff members are always expected to lock their computers when not attended. The WARU email account is only accessed by authorised individuals. The Gatekeeper regularly changes the password to enable access. Email addresses of study participants will be recorded, and study specific emails will be diverted to a secure named folder, only accessed by the immediate WARU Team. Each Aberystwyth University computer is scheduled to perform daily updates for anti-virus and firewall protection, this aims at keeping the university network, bug, and virus free. In the event of a power surge the university's network is backed up every 15 minutes therefore content is regularly saved automatically on the universities back up drive. Confidential data will not be stored on mobile devices (phones, laptops, tablets). If for any reason confidential data needs to be stored on a mobile device then permission must be gained from the line manager first, and if granted, all documents will be encrypted. For participant confidentiality, all personal data such as names, addresses, DOB and phone numbers, will be stored and password protected and there will be a gatekeeper of the password. Personal details will be removed or replaced with an ID code when data is being analysed. Only the gatekeeper can link names to codes. Sensitive materials (participant's details e.g., address) will be electronically stored away and access will be restricted. This data will be password protected and there will be a gatekeeper of the password. ID codes are completely randomised. The researchers will select 4 digits to create random codes which can then be assigned to participants, alongside the study start code. All rooms where data is stored will only be accessible via a card key. This will prevent those who are not authorised gaining access into a room where sensitive data (e.g., consent forms) may be. In exceptional circumstances, confidentiality may have to be breached in cases where persons are considered to be at risk or if required by law.

9.3) Data analysis and statistics

Data analysis will be conducted at Aberystwyth University. Chemical composition using metabolomics will be conducted at AberInnovation and Aberystwyth University, and the quantification of short chain

GDPR: For the data the Welsh Government requires, Welsh Government is the data controller and Aberystwyth University (WARU) is the data processor. For any other data, including sensitive personal data, the data controller and the data processor is Aberystwyth University (WARU).

fatty acids as well as clinical biochemistry (Chem21 to include glucose and lipid panel tests) will be analysed at Bronglais hospital.

GDPR: For the data the Welsh Government requires, Welsh Government is the data controller and Aberystwyth University (WARU) is the data processor. For any other data, including sensitive personal data, the data controller and the data processor is Aberystwyth University (WARU).

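### Stool form is measured to monitor laxative effects but is scheduled only before any tea and at the final visit, so effects that resolve earlier or lead to stopping may go unrecorded

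*Protocol*

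**What the plan says.** **Purpose.** Section 5.1 of the Protocol states: "Researchers will measure stool consistency using the Bristol Stool Form Scale, to monitor laxative effects". Section 1 gives the wider interest: "They would like to explore if consumption of the teas for 21 days has an impact on digestion and potentially help control weight gain".

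**Timing.** Section 1 states: "Diet data, stool consistency and anthropometric measurements will be collected pre and post intervention". Section 5.6 carries this out. At the first morning visit, "The researcher will ask the participant to record their stool consistency using the Bristol stool scale and record their diet using the PDQS questionnaire". The same sentence appears again for the final visit. At the first visit, "The participant will also collect the allocated tea bags".

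**The 21 days.** Section 5.6 asks participants to "consume a cup of hot-infused tea after their last meal/snack of the day (post 6pm) daily, for 21 days". It gives preparation instructions and adds: "Whilst undergoing the experimental sessions, if necessary, the researcher will be easily contacted by email, Teams or phone". It asks for no stool record in this period. The post-study contact collects only the diet questionnaire and weight.

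**Stopping and illness.** Section 6 says the ingredients have already been tested for adverse effects, "however if any negative effects occur, participants are asked to refrain from continuing in the study". Under section 9.1, a participant who becomes unwell must alert the team at once and is suspended until the matter has been discussed. The team can also monitor health remotely over 14 days. Neither section asks for a stool-form record.

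**The concern.** Two of the three arms contain senna or rhubarb root, and the Bristol scale is the measure meant to show laxative effects. A single record after three weeks of tea shows best an effect that is still present at the final visit, in people who attend it. Two groups can be missed:

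- participants whose stools loosened and then returned to normal before the final visit;
- participants who stopped because of the effect and gave no later stool record.

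If either group is larger in the senna or rhubarb root arm than in the green tea arm, the final-visit comparison is pulled towards no difference. This is a matter of data collection, so an analysis plan could not recover it afterwards. What is at stake is the digestive reading of the trial, not its lipid objectives.

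**Working it through.** The protocol has no figure of its own to reproduce. The check is of the schedule, followed by an illustration.

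**Step 1. Stool-form records specified per participant**

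| Time | Stool form specified? | Source |
|---|---|---|
| First visit, morning | Yes, one record | 5.6 |
| Daily tea period | None | 5.6 |
| On stopping for a negative effect | None | 6 |
| On becoming unwell | None | 9.1 |
| Final visit, morning | Yes, one record | 5.6 |
| Post-study contact | None | 5.6 |

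The tea is collected at the first visit and drunk after 6pm, so the first record precedes any tea.

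**Step 2. Could the text mean continuous recording?** Read alone, the first-visit sentence might. But it recurs at the final visit, and section 1 says pre and post. The stool ranking criterion in section 5.3 gives no frequency. Two time points is the supported reading.

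**Step 3. Counts, with 55 participants (section 5.2)**

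- Scheduled stool records: 2 x 55 = 110, of which at most 55 follow any tea.
- Scheduled tea evenings: 21 x 55 = 1,155.

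These counts give no coverage percentage, because the period a visit record covers is not stated.

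**Step 4. Illustration of the mechanism.** All rates here are assumed; the protocol gives none. Take 18 per arm (55/3 = 18.3; the allocation ratio is not stated). On green tea, 1 of 18 is affected (5.6%), is still affected at the final visit, and nobody stops.

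*Stopping.* Suppose affected participants who stop give no final record.

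- 5 of 18 affected in a laxative arm: 27.8% - 5.6% = 22.2 points.
  - One stops: 4/17 = 23.5%, difference 18.0 points.
  - Two stop: 3/16 = 18.8%, difference 13.2 points.
  - Three stop: 2/15 = 13.3%, difference 7.8 points.
- 3 of 18 affected: 16.7% - 5.6% = 11.1 points.
  - One stops: 2/17 = 11.8%, difference 6.2 points.
  - Two stop: 1/16 = 6.3%, difference 0.7 points.

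*Resolution.* Suppose all attend and the final record reflects only that time. If 5 of 18 were affected but two have recovered, 3/18 = 16.7% is seen, and the difference falls from 22.2 to 11.1 points.

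The illustration shows direction and mechanism under these assumptions. It does not estimate the loss in this trial.

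**The case against.** The strongest reply is that nothing here is misstated. Stool form is neither the primary nor the labelled secondary objective and has no hypothesis. Section 7 describes the work as a pilot. Tea is taken every evening, so a pre/post comparison does address an effect that persists under habitual use. Sections 4 and 6 mention a laxative effect only for large quantities taken in one go. The illustrative rates are invented, and assuming no green tea stoppers fixes the direction of the bias. Even the undiluted case, 5/18 against 1/18, gives a two-sided Fisher p of about 0.18, so complete records would still be inconclusive. All of this stands. It limits the weight of the point and means any summary should be descriptive. It does not remove the gap between the stated purpose and the schedule.

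A reader might also infer more than the protocol supports:

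- **That the protocol contradicts itself.** It does not. Section 5.1 also uses the word monitor for the microbiota, which is sampled before and after.
- **That the final record cannot show an earlier effect.** The period it covers is unstated, so a record reaching back is not excluded. The supportable wording is that it may not show one.
- **That only spontaneous reports are possible.** Section 9.1 goes further, with an instruction to alert the team, a discussion and possible remote monitoring. Section 5.6 also asks participants to report any over-the-counter medication they need. What is missing is a stool-form record.
- **That everyone who stops is lost to the final visit.** Whether they would still attend is not stated.

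**Conclusion.** The point holds as a limit of the assessment schedule. A measure included to follow laxative effects has one scheduled record after tea, with no stated period of coverage and none tied to stopping or illness. A final-visit comparison could therefore understate laxative effects in the senna or rhubarb root arms against green tea.

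That direction depends on transient effects, or stopping because of them, being commoner in those arms, and on stoppers giving no later record. The protocol neither establishes nor rules out either condition. The size is unknown. The lipid, HDL, diet, short chain fatty acid and microbiome objectives do not depend on this measure. The change is worth making because it is cheap and the data cannot be recovered later, not because the main conclusions are at risk.

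**What to change.** In sections 5.1 and 5.6:

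1. Give each participant the Bristol scale and a one-page home record no later than the first visit, to complete daily until day 21 or until they stop. The handover should be explicit: the scale is listed among the induction materials, but induction may be by phone or Teams, so possession beforehand is not established.
2. Ask for a stool-form entry at the time of stopping. For participants who are unwell, take it during the contact that section 9.1 already provides for. For others who stop under section 6, collect the home record up to that day.
3. State the period that each of the two visit records covers.
4. Before unblinding, state which scale types count as loose.
5. Summarise loose-stool days and the number stopping by randomised arm, including early stoppers, alongside the two visit records. Label the summary descriptive.

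This concerns recording only and leaves the rules on stopping and suspension as they are.

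**Cost.** A small daily burden, and data entry for up to 21 x 55 = 1,155 extra entries on top of the 110 visit records. Participants must be told in advance, since the stool ranking criterion in section 5.3 does not clearly cover daily entries. No extra visit or procedure is needed.

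### Antibiotic use before the baseline stool sample is neither screened nor recorded, which weakens the pre/post microbiome comparison, mainly through lost precision

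*Protocol*

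**What the plan says.** Antibiotics appear once in the protocol, as the last inclusion criterion in section 5.3: participants must be "Able to inform the researcher if any antibiotics or heavy alcohol is consumed over the intervention period". This is a duty to report, and its window opens when the tea starts.

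Nothing else reaches back before baseline for antibiotics:

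- In section 5.4 the nearest exclusions are "Serious health conditions that require daily long-term medications (including immunosuppressants" and "Diagnosed with a serious health condition within the last 12 months". A short course that has already finished meets neither. Section 5.5 adds only COVID-related criteria and a further line on daily long-term medication.
- The monitoring stage in section 5.6, a "period (two days before the study", concerns over-the-counter products and herbal supplements. Antibiotics are not named.
- The first visit in section 5.6 lists blood, stool, weight, height, stool scale and diet questionnaire, but no medication history.

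For the 16S data, section 5.1 says that "alpha and beta indices representing community structure will be compared between the pre and post intervention samples (and between treatments"), and that the researchers will look for microbes "that are boosted or depleted in response to the tea".

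**The concern.** The protocol treats antibiotics as worth knowing about, but sets the reporting window so that it misses the period that shapes the baseline stool sample. A participant who finished a course shortly before the first visit is eligible and unidentified. Any recovery of that person's gut flora over the next 21 days appears as a pre-to-post change, and the plan reads pre-to-post change as a response to the tea.

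Randomisation does not protect a within-arm pre/post contrast. It balances earlier use between arms only in expectation, and the arms are small. A SAP could deal with antibiotic use reported during the 21 days, because that information reaches the researchers. It could not deal with earlier use, because nothing in the protocol collects it. Eligibility and baseline data collection belong in the protocol, so this is not a detail left for the SAP.

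**Working it through.** The protocol gives no effect size, SD, power or antibiotic prevalence, so there is no figure to reproduce. The calculation below only sizes the problem.

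**Inputs**

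- From the protocol: 55 participants (section 5.2) and three randomised groups (section 5.6).
- Assumed: equal allocation, 55/3 = 18.3, taken as n = 18 per arm. No ratio is stated.
- Assumed: a proportion p = 3% to 8% with a recent course.
- Assumed: an affected person's index moves by s = 2 to 3 SD of change.

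**How many affected people to expect in an arm of 18**

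- At least one: 1 − (1 − p)^18. At 3%, 1 − 0.97^18 = 0.42. At 8%, 1 − 0.92^18 = 0.78.
- Two or more: subtract 18p(1 − p)^17 as well. At 3% this gives 0.10; at 8%, 0.43.

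The chance of at least one among all 55 is higher, 1 − (1 − p)^55 = 0.81 to 0.99, but the pre/post contrast is made within an arm, so the per-arm figures are the relevant ones.

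**What k affected people do to the arm's mean change**

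Mean shift = k·s/18. Variance factor = 1 + (k/18)(1 − k/18)s².

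| k | s | Mean shift (SD) | Variance factor |
|---|---|---|---|
| 1 | 2 | 0.11 | 1.21 |
| 1 | 3 | 0.17 | 1.47 |
| 2 | 2 | 0.22 | 1.40 |
| 2 | 3 | 0.33 | 1.89 |

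The standard error of a mean change at n = 18 is 1/√18 = 0.24 SD. One affected person therefore moves the mean by about 0.5 to 0.7 standard errors, and two by about 0.9 to 1.4.

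**Effect on a test**

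Simulated: one-sample t-test on change, n = 18, nominal two-sided 5%, 200,000 runs.

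*No tea effect, proportion significant*

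- One affected person: 4.9% (s = 2), 4.6% (s = 3).
- Two moving the same way: 7.9% (s = 2), 8.7% (s = 3).
- Two moving in opposite directions (+3 and −3): 0.6%.

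*True effect set at 0.70 SD, which gives 80% power when nobody is affected*

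- One person moving against the effect: power falls to 58% (s = 2) or 40% (s = 3).
- One person moving with the effect: power rises to about 85–86%, but the estimated effect is then too large by the shift in the table.

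A single affected person therefore leaves the false-positive rate at about 5%, because the added variance offsets the shift in the mean. What suffers is precision and, when the person moves against the effect, power.

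**The case against.** A reader might infer that the pre/post comparison will readily mistake antibiotic effects for tea effects. The numbers do not support that. One affected person does not raise the false-positive rate, and even two moving together raise it only to about 8–9%. On the stated assumptions two or more in an arm has a 10–43% chance, and opposite movements make the test conservative. This part of the objection stands. It has two limits: the simulation concerns a single index, such as an alpha-diversity measure, not every taxon; and people recovering from earlier courses may tend to move in the same direction, so cancellation cannot be relied on.

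A reader might also infer that someone treated with antibiotics during the 21 days simply carries on. The protocol does not say so. Section 9.1 suspends participation of anyone who becomes unwell until the research team has discussed it, and section 5.3 makes the use reportable. How such samples enter the microbiome analysis is ordinary SAP content, and no SAP was available for this review. That part cannot be held against the protocol.

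Finally, the primary objective and the objective labelled secondary are both lipid outcomes (section 5.1), section 7 describes the work as a pilot, and a between-treatment microbiome comparison is also planned, in which earlier use is balanced on average. All of this lowers the severity. None of it supplies the missing baseline information.

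**Conclusion.** The point holds in a limited form. Antibiotic use before the baseline stool sample is neither an exclusion nor a recorded item, and the gap cannot be repaired at analysis. If 3–8% of participants have had a recent course, an arm of 18 has a 42–78% chance of containing at least one. Such a person moving by 2–3 SD inflates the variance of change by 21–47% and shifts the arm mean by 0.11–0.17 SD. The consequence is chiefly lost precision and power, with some bias; a modest rise in false attribution needs two or more in one arm moving the same way. These sizes rest on the assumed prevalence, the assumed shift and equal allocation. That earlier use goes unrecorded rests on the protocol text alone. Because the endpoint is exploratory, this is a desirable improvement and not a threat to the trial's main question.

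**What to change.** Add to section 5.4 an exclusion for systemic antibiotic use within a look-back period before baseline. The investigators should set its length before enrolment, and it can be asked as one question at the pre-induction call. If an exclusion is thought too restrictive, at minimum record the use at the first visit as a covariate for the microbiome analysis. Participants who report antibiotics during the 21 days stay in the lipid analysis; the handling of their stool samples can be left to the SAP.

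The cost is one screening question and one eligibility line, with slightly slower recruitment if the exclusion is chosen.
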